#### Visit 10 (Day 407): Safety follow-up Visit

The following will be performed/collected:

- Physical examination, including weight (kg) (see [Section 5.3.1](#))
- ESR and CRP
- Vital signs (blood pressure, pulse rate, respiratory rate, and body temperature; see [Section 5.3.2](#))
- Urine pregnancy test for women of child-bearing potential
- Laboratory testing (serum chemistry, hematology and urinalysis; see [Section 5.3.3](#))
- 12-lead ECG (see [Section 5.3.4](#))
- Previous and concomitant therapy (see [Section 4.2](#))
- Assessment of AEs (see [Section 5.3.6](#))
- Review of patient diary card entries
- Blood PPK sample (see [Section 5.4](#))
- Blood samples for the level of ADAs and nADAs (see [Section 5.6.1](#))
- End of participation

### **6.2.3 Follow-Up Period and Trial Completion**

#### End of Treatment Visit

Patients who discontinue the trial at any time after Day 1 (but do not withdraw their consent) will be required to have all of the evaluations for the Week 48 Visit as soon after trial discontinuation as possible.

Every effort should be made for all patients who complete the total 48-week treatment period or who discontinue the trial early, to return for a safety follow-up visit 10 weeks after the last dose of trial medication.

#### End of trial definition

The trial will be considered to be complete once the last patient in the trial meets one of the following:

- Completes the last trial visit (Week 58 or safety follow-up visit 10 weeks after the last trial medication administration); or
- Dies; or
- Is lost to follow-up

The Sponsor may also elect to discontinue clinical investigations under this trial for any reason at any time.

#### Unscheduled Visit Assessments

Patients may attend the trial site for unscheduled visits at any time for additional safety monitoring at the discretion of the Investigator.

## **7. STATISTICAL METHODS AND DETERMINATION OF SAMPLE SIZE**

### **7.1 STATISTICAL DESIGN - MODEL**

This is a Phase IIIb, open-label, single arm extension of Trial 1297.2.

The objective of this trial is to provide long-term efficacy, safety, PK and immunogenicity data on BI 695501 administered via prefilled syringe in patients with RA who have completed the trial 1297.2.

No formal hypothesis testing will be performed. The analysis of the data will be performed descriptively.

### **7.2 NULL AND ALTERNATIVE HYPOTHESES**

No formal hypothesis testing will be performed. If confidence intervals or p-values are presented, they will be interpreted in an exploratory fashion only.

### **7.3 PLANNED ANALYSES**

All patients treated with at least one dose of trial medication during the 1297.3 trial (Safety Analysis Set) will be included in the safety evaluations.

The Full Analysis Set (FAS) will be the basis for efficacy analyses. The FAS consists of all patients who received at least one dose of trial medication in Trial 1297.3 and had at least one DAS28 (ESR or CRP) or ACR20 measured during the 1297.3 trial.

The “All Enrolled Patients” analysis set will include all patients who provide informed consent for this trial.

For presentation of results in the report, three groups of patients will be created depending on treatments assigned in Trial 1297.2. The first group will consist of patients who were randomized to BI 695501 in Trial 1297.2 and will continue to receive BI 695501 in Trial 1297.3 but via self-administration. The second group will consist of patients who were initially randomized to receive US-licensed Humira® in Trial 1297.2, continue to receive US-licensed Humira® after Week 24 re-randomization in Trial 1297.2 and will transition to BI 695501 via self-administration in the Trial 1297.3. The third group will consist of patients who were initially randomized to receive US-licensed Humira® in Trial 1297.2, transitioned to BI 695501 following the re-randomization at Week 24 in the Trial 1297.2 and continue to receive BI 695501 in Trial 1297.3 but via self-administration. [Table 7.3: 1](#) gives an overview of the above-defined patient groups.

Table 7.3: 1 Patient groups for presentation of analysis results

| Patient group                              | 1  | 2            | 3            |
|---|-----------|---------------------|---------------------|
| Randomized treatment in Trial 1297.2              | BI 695501 | US-licensed Humira® | US-licensed Humira® |
| Re-randomized treatment in Trial 1297.2 (Week 24) | BI 695501 | US-licensed Humira® | BI 695501           |

The descriptive statistics for safety, efficacy and other endpoint will be presented for these three groups and overall for all patients combined.

Unless otherwise specified, baseline for this trial (1297.3) is defined as the baseline of Trial 1297.2 and all endpoints are those assessed in Trial 1297.3.

### **7.3.1 Primary endpoint analyses**

The primary endpoint is defined as the number (proportion) of patients with drug-related AEs during the treatment phase.

The primary safety analysis will be performed using the Safety Analysis Set.

All AEs with an onset date between start of treatment and end of the REP, a period of 10 weeks after the last dose of trial medication, will be assigned to the treatment phase for evaluation. Adverse events will be classified by system organ class and term using the Medical Dictionary of Regulatory Activities (MedDRA) coding dictionary.

The proportion of patients with drug-related AEs during the treatment phase will be analyzed descriptively by MedDRA system organ class and preferred term. In addition, patient incidence and/or event incidence per 1000 patient-years exposure will be provided. No formal inferential analyses are planned.

### **7.3.2 Secondary endpoint analyses**

The secondary efficacy endpoints (see [Section 5.1.2](#)) will be summarized descriptively for the FAS.

#### **7.3.4 Safety analyses**

Adverse events will be coded using the MedDRA coding dictionary. Standard BI summary tables and listings will be produced. All AEs with an onset between start of treatment and end of the residual effect period (REP), a period of 10 weeks after the last dose of trial medication, will be assigned to the treatment period for evaluation.

All treated patients will be included in the safety analysis. In general, safety analyses will be descriptive in nature and will be presented by MedDRA system organ class and preferred term. No hypothesis testing is planned.

Statistical analysis and reporting of AEs will concentrate on treatment-emergent AEs. To this end, all AEs occurring between start of treatment and end of the REP will be considered 'treatment-emergent'. Adverse events that start before first drug intake and deteriorate under treatment will also be considered as 'treatment-emergent'.

Frequency, severity, and causal relationship of AEs will be tabulated by system organ class and preferred term after coding according to the current version of the MedDRA.

In addition, for infections/serious infections, hypersensitivity reactions, drug-induced liver injury (DILI) and injection-site reactions, patient incidence and/or event incidence per 1000 patient-years exposure will be displayed.

Laboratory values taken after the first dose of trial medication up to a period of 10 weeks after the last dose of the trial medication will be assigned to the treatment phase for evaluation. Laboratory data will be analyzed both quantitatively as well as qualitatively. The latter will be done via comparison of laboratory data to their reference ranges. Values outside the reference range as well as values defined as clinically relevant will be highlighted in the listings. Treatment groups will be compared descriptively with regard to distribution parameters as well as with regard to frequency and percentage of patients with abnormal values or clinically relevant abnormal values.

Vital signs (blood pressure, pulse rate, respiratory rate and body temperature), physical examinations, 12-lead ECGs, or other safety-relevant data observed at screening, baseline, during the course of the trial and at the end-of-trial evaluation will be assessed with regard to possible changes compared to findings before start of treatment.

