### 3.3. CHANGES TO ANALYSIS FROM PROTOCOL

No change is planned.

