## 16.3. LABORATORY EVALUATIONS

Results from the central laboratory will be included in the reporting of this trial for Serum Chemistry, Hematology and Urinalysis. A list of laboratory assessments to be included in the outputs is included in APPENDIX 4.

Presentations will use SI and US Units.

Quantitative laboratory measurements reported as "< X", i.e. below the lower limit of quantification (BLQ), or "> X", i.e. above the upper limit of quantification (ULQ), will be converted to X for the purpose of quantitative summaries, but will be presented as recorded, i.e. as "< X" or "> X" in the listings.

Qualitative laboratory urinalysis results measured by central laboratory will be classified to the categories "Positive" and "Negative" based on the central laboratory normal reference.

The handling of retests, unscheduled and end of trial measurements is described in Section 6.3. However, laboratory values taken after the first dose of trial medication up to a period of 10 weeks after the last dose of the trial medication will be assigned to the treatment phase for evaluation. All available data will be listed.

The following summaries will be provided for laboratory data:

- Actual and change from baseline in trial 1297.2 by visit (for quantitative measurements)

---

Document: \\ieedc-nas01a\BIOSdata\Boehringer\_Ingelheim\BI\_695501\NVA96235\Biostatistics\Documentation\SAP\10  
v1.0\BI\_1297.3\_SAP\_22JUN2016\_v1.0

Author: Version Number: 1.0  
Version Date: 22JUN2016

Template No: CS\_TP\_BS016 – Revision 3  
Effective Date: 01May2012

Reference: CS\_WI\_BS005

- Shifts in Rheumatology Common Toxicity Criteria (RCTC) grading, from baseline in trial 1297.2 by visit (for gradable parameters, see APPENDIX 4)
- Shifts from baseline category (Low/ Normal/ High) in trial 1297.2 by visit (for non-gradable parameters except urinalysis parameters and ADA)
- Shift from baseline category (Negative/ Positive) in trial 1297.2 by visit (for urinalysis non-gradable parameters)
- Box plots for ESR, CRP, hemoglobin, leukocytes (equivalent to white blood cells), platelets, AST, ALT, bilirubin, creatinine, cholesterol
- Plots for time course of gradable safety parameters for subjects having at least one value with toxicity grade 3 or 4 (RCTC grading is described section 16.3.3)
- Proportion and frequency of possible Hy's law subjects
- Proportion and frequency of possible Drug Induced Liver Injuries

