## **16.4. ECG EVALUATIONS**

Results from ECGs will be summarized by visit to the categories as recorded in the eCRF page "12-Lead-ECG" ("normal", "abnormal, not clinical significant" and "abnormal, clinical significant").

Document:	\ieedc-nas01a\BIOSdata\Boehringer_Ingelheim\BI_695501\NVA96235\Biostatistics\Documentation\SAP\10\v1.0\BI_1297.3_SAP_22JUN2016_v1.0		
Author:	Version Number:	1.0	Version Date: 22JUN2016

Template No: CS\_TP\_BS016 – Revision 3  
Effective Date: 01May2012

Reference: CS\_WI\_BS005

---

ECG evaluations will also be listed.

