## 16.5. VITAL SIGNS

The following Vital Signs measurements will be reported:

- Sitting Systolic Blood Pressure (mmHg)
- Sitting Diastolic Blood Pressure (mmHg)
- Sitting Pulse Rate (bpm)
- Sitting Respiratory Rate (breaths/min)
- Temperature (°C)

The weight will be presented along with vital signs.

- Weight (kg)

The handling of retests, unscheduled and end of trial measurements is described in Section 6.3.

The summary of actual and change from baseline by visit will be provided for vital sign data. In case of multiple measurement timepoints at one visit the pre-injection data will be used for summary tables.

Vital signs data will be listed.

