## 16.6. PHYSICAL EXAMINATION

Proportion of evaluation categories (normal, abnormal) at baseline and post-baseline visits will be provided for physical examination data.

The handling of retests, unscheduled and end of trial measurements is described in Section 6.3.

Baseline is described in Section 6.2.

Physical examination data will be listed.

---

Document: \\ieedc-nas01a\BIOSdata\Boehringer\_Ingelheim\BI\_695501\NVA96235\Biostatistics\Documentation\SAP\10  
v1.0\BI\_1297.3\_SAP\_22JUN2016\_v1.0

Author: Version Number: 1.0  
Version Date: 22JUN2016

Template No: CS\_TP\_BS016 – Revision 3  
Effective Date: 01May2012

Reference: CS\_WI\_BS005

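### SAP 16.4 and 16.6 plan per-visit ECG and physical-examination counts without within-patient change, so the summary tables cannot show how many patients became abnormal

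*Protocol*

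**What the plan says.** Protocol 7.3.4 groups vital signs, physical examinations, 12-lead ECGs and other safety-relevant data, and says that they "will be assessed with regard to possible changes compared to findings before start of treatment".

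The SAP turns this into outputs as follows:

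- **Vital signs (16.5):** "The summary of actual and change from baseline by visit will be provided for vital sign data".
- **Laboratory data (16.3):** change from baseline for quantitative values, and shift tables such as "Shifts from baseline category (Low/ Normal/ High) in trial 1297.2 by visit". There is a separate negative/positive shift for urinalysis.
- **ECG (16.4):** "Results from ECGs will be summarized by visit to the categories as recorded in the eCRF page". The categories are normal, abnormal but not clinically significant, and abnormal and clinically significant. In addition, "ECG evaluations will also be listed".
- **Physical examination (16.6):** "Proportion of evaluation categories (normal, abnormal) at baseline and post-baseline visits will be provided for physical examination data". In addition, "Physical examination data will be listed".

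SAP 6.3 leaves unscheduled and early-termination data out of by-visit tables. SAP 3.3, on departures from the protocol analysis, says "No change is planned".

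**The concern.** Change from a pre-treatment finding is a question about each patient: was this patient normal before the first dose and abnormal afterwards? For a categorical assessment, the percentage abnormal at each visit does not answer it. A patient who becomes abnormal and a patient who normalises cancel out, and the two rows look the same as if nobody had changed. The SAP handles this for laboratory categories, including the simple positive/negative urinalysis results, but its text does not do so for ECG or physical examination.

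At stake is the reading of two secondary safety assessments. Similar percentages before and after could be taken as no change when the table cannot distinguish that from offsetting movement. For physical examination, the early-termination assessment of patients who stop treatment is also missing from the by-visit table. The baseline and later percentages then rest on different patients, and even the net change is blurred.

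**Working it through.** The documents give no figure to reproduce: there is no power calculation, and no expected abnormality rate for either assessment. The check has two parts.

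**1. Commitment against planned output**

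| Assessment | Protocol 7.3.4 asks for change from pre-treatment | Within-patient change in the SAP text |
|---|---|---|
| Vital signs | yes | yes (16.5) |
| Physical examination | yes | no; per-visit proportions and a listing (16.6) |
| 12-lead ECG | yes | no; per-visit categories and a listing (16.4) |
| Laboratory data | handled separately in the same section | yes; changes and shifts (16.3) |

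**2. What per-visit counts can and cannot determine**

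Let *N* patients be assessed at both times, *a* abnormal before and *b* abnormal after. Let *x* be the number newly abnormal and *y* the number who normalise.

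- The counts fix only the balance: b = a + x − y, so x = b − a + y.
- Since y lies between 0 and a, and x between 0 and N − a, the number newly abnormal can be anything from max(0, b − a) to min(b, N − a).

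Inputs: *N* of 300 to 400 is the anticipated enrolment in protocol 7.7, and 350 is its midpoint. The abnormality rates are assumptions.

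For N = 350 and 10% abnormal at both times, a = b = 35 and N − a = 315. The lower limit is max(0, 0) = 0 and the upper limit is min(35, 315) = 35. As a share of patients normal at baseline this is 0 to 35/315 = 11.1%.

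| Abnormal before → after | N = 300: newly abnormal | N = 400: newly abnormal | Share of baseline-normal patients |
|---|---|---|---|
| 5% → 5% | 0 to 15 of 285 | 0 to 20 of 380 | 0 to 5.3% |
| 10% → 10% | 0 to 30 of 270 | 0 to 40 of 360 | 0 to 11.1% |
| 20% → 20% | 0 to 60 of 240 | 0 to 80 of 320 | 0 to 25.0% |
| 10% → 12% | 6 to 36 of 270 | 8 to 48 of 360 | 2.2 to 13.3% |

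In the last row the planned table would show a net rise of 6 or 8 patients, while the number newly abnormal could be up to six times that (36/6 = 48/8 = 6). Splitting abnormal ECGs by clinical significance does not remove the problem, because the three rows are still per-visit totals.

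**Schedule.** In the protocol flow chart, ECGs are taken at Screening, Baseline and the safety follow-up (Day 407) only, so there is one scheduled pre/post comparison. Physical examinations are done at Screening, Baseline, Weeks 12, 24 and 48, and the safety follow-up.

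**The case against.** The strongest reply has five parts.

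- **The protocol wording is general.** It names no table or method, and the section calls safety analyses descriptive. Counts at baseline and later visits, with listings, are a descriptive comparison of a kind. This stands in part: a reader might infer that SAP 3.3 is false in declaring no change, but the documents do not go that far. What remains is that the planned summaries answer the within-patient question for vital signs but not for these two assessments.
- **New findings that matter are captured elsewhere.** Protocol 5.3.7 requires ECG and physical-examination changes judged clinically relevant to be recorded as adverse events, and treats pre-existing abnormalities as baseline conditions. Protocol 5.3.4 says much the same for ECG. These events reach the treatment-emergent tables. This stands, and it limits the gap mainly to new abnormalities not judged clinically relevant.
- **Patient listings are planned.** True, so nothing is lost from the record. A reader would, however, have to count transitions by hand across 300 to 400 patients.
- **The table templates are not in the documents.** SAP 8 says that they set the format and content of the outputs. They may already contain a shift layout, and this cannot be excluded.
- **The rates are assumed, and the upper limit is extreme.** Reaching 35 newly abnormal patients requires all 35 baseline-abnormal patients to normalise. This stands: the range shows what the tables leave open, and is no evidence that masking is likely.

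**Conclusion.** The point holds as a minor reporting gap. On the SAP text, the ECG and physical-examination summaries show net change only, leave out early-termination and unscheduled assessments, and so cannot give the number of patients who became abnormal. Under an assumed 10% abnormal at both times in 350 patients, that number could be anywhere from 0 to 35 (0 to 11.1% of those normal at baseline). The range scales with the assumed rate and takes the same patients as assessed at both times.

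A reader might go further and infer that new abnormalities would go undetected, or that a safety signal is being concealed. The documents do not support that: clinically relevant changes go to the adverse-event tables, clinically significant ECGs have their own row, and all results are listed by patient. The conclusion also depends on the unseen templates not already providing a shift table. The primary endpoint is unaffected.

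**What to change.** In SAP 16.4 and 16.6, add a within-patient shift table by 1297.2 treatment group and overall.

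- **Rows:** the last category recorded before the first 1297.3 dose, with this baseline stated explicitly. SAP 6.2 uses both a 1297.2 and a 1297.3 baseline, 16.4 names neither, and 16.6 only points to 6.2. The pre-dose 1297.3 value matches the protocol's reference to findings before treatment starts, but differs from the 1297.2 default in protocol 7.3 and from the laboratory shifts, so the choice needs a sentence.
- **ECG columns:** the safety follow-up assessment, and a worst post-baseline category that also counts any unscheduled ECG.
- **Physical-examination columns:** each post-baseline visit, and the worst post-baseline category including early-termination assessments.
- **Summary line:** the number and percentage newly abnormal among patients normal at baseline.

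The cost is SAP wording and the programming of two descriptive tables from data already collected; no test is needed. If the templates already contain these shifts, one sentence in each of 16.4 and 16.6 closes the point.

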#### **7.3.5 Pharmacokinetic analyses**

A PPK analysis with sparse blood sampling throughout the treatment period and at follow-up will be carried out to assess the PK of BI 695501. The PK analysis might involve combining data with data from other BI 695501 studies. If relevant, a relationship will be investigated between selected safety and efficacy parameters including the development of ADA/nADA. The population PK will be described in a separate analysis plan and will be reported separately to the CTR. Raw concentration data will be reported in the CTR. Reporting of the raw concentration data will be described in the trial statistical analysis plan (TSAP).

### 7.3.6 Immunogenicity analyses

If data allow, the antibody response, antibody titer and neutralizing antibody response will be summarized as appropriate (frequency/proportions for ADA positive samples, descriptive statistics for titer and frequency/proportions of characterization of the neutralizing potential of the ADA for ADA positive samples assayed) by scheduled assessments (Week 12, Week 24 and Week 48) and overall (for ADA positive patients only). Further, the potential relationship between safety and antibody response will be explored if appropriate. Details of the analyses will be described in the TSAP.

## 7.4 INTERIM ANALYSES

No formal interim analysis will be performed for this trial. However, based on regulatory requirements safety snapshots may be provided.

## 7.5 HANDLING OF MISSING DATA

### 7.5.1 Safety and other endpoints

For the aim of primary and secondary analyses, in case of missing AE relationship status, the AE will be considered as related.

For other endpoints, rules for the handling of missing data will be specified in the TSAP if necessary.

### 7.5.2 Efficacy endpoints

Missing ACR20 data will be imputed using the last observation carried forward (LOCF) method. However, all patients who discontinue treatment, are lost-to-follow-up or have any severe violation related to any therapy that may significantly impact efficacy assessment ([Table 4.2.2.1: 1](#)) prior to the secondary endpoint assessment will be considered as a non-responder. This is referred to as 'NRI' (missing data imputation of primary analysis in 1297.2).

. For missing data, LOCF will be applied on the component variables prior to the DAS28(ESR) score.

Other missing efficacy data will not be imputed.

Further details will be given in the TSAP.

## 7.6 RANDOMISATION

This is an open-label, single-arm trial. No randomization will be performed.

## **7.7 DETERMINATION OF SAMPLE SIZE**

All patients from the initial randomized controlled Trial 1297.2 willing and able to self-administer BI 695501 pre-filled syringe, and who are eligible for further treatment courses will be offered an additional treatment course with BI 695501. Patients are deemed eligible for further treatment courses if they have not experienced Investigator-reported drug-related SAEs during the 1297.2 trial, and in the Investigator's assessment can benefit from receiving BI 695501. It is anticipated that approximately 300 to 400 patients will be eligible to participate in this roll-over extension trial.

